2 PROTOCOL SYNOPSIS

Title A Phase 2, Randomized, Double-blind, Controlled Study to Evaluate the Safety and Efficacy of VX-121 Combination Therapy in Subjects Aged 18 Years and Older With Cystic Fibrosis

Brief Title A Study to Evaluate the Safety and Efficacy of VX-121 Combination Therapy in Subjects With Cystic Fibrosis

Clinical Phase and Clinical Study Type Phase 2, safety and efficacy

Objectives Primary Objectives

Parts 1 (Subjects with F/MF genotypes) and 2 (Optional; Subjects with the F/F genotype)

- To evaluate the safety and tolerability of VX-121 in triple combination (TC) with tezacaftor (TEZ)/VX-561 (deuterated ivacaftor [IVA])
- To evaluate the efficacy of VX-121 in TC with TEZ/VX-561

Secondary Objectives

Parts 1 and 2

- To evaluate the pharmacodynamic (PD) effect of VX-121 in TC with TEZ/VX-561
- To evaluate the pharmacokinetics (PK) of VX-121 when administered in TC with TEZ/VX-561
- To evaluate the PK of TEZ, VX-561, and their respective metabolites when administered in TC with VX-121

Endpoints Primary Endpoints

- Safety and tolerability, based on the assessment of adverse events (AEs), laboratory test results, standard 12-lead ECGs, vital signs, and spirometry
- Absolute change in percent predicted forced expiratory volume in 1 second (ppFEV₁) from baseline through Day 29

Secondary Endpoints

- Absolute change in sweat chloride concentrations from baseline through Day 29
- Absolute change in Cystic Fibrosis Questionnaire-Revised (CFQ-R) respiratory domain score from baseline at Day 29
- PK parameters of VX-121, TEZ, VX-561, [REDACTED] and relevant metabolites

- Number of Subjects** Approximately 108 subjects (including optional parts): 54 in Part 1, 27 in Part 2, [REDACTED]
- Study Population** **Parts 1** [REDACTED] Male subjects and female subjects with cystic fibrosis (CF), heterozygous for *F508del* and a minimal *CFTR* function mutation that is not responsive to TEZ, IVA, or TEZ/IVA (F/MF genotypes), ages 18 and older
Part 2: Male subjects and female subjects with CF, homozygous for *F508del* (F/F genotype), ages 18 and older
- Investigational Drug** **Active substance:** VX-121
Activity: CFTR corrector (increased Cl⁻ secretion)
Strength and route of administration: 5-mg tablet for oral administration
- Active substance:** TEZ (VX-661)
Activity: CFTR corrector (increased Cl⁻ secretion)
Strength and route of administration: 50-mg TEZ tablet for oral administration
- Active substance:** VX-561
Activity: CFTR potentiator (increased Cl⁻ secretion)
Strength and route of administration: 50-mg VX-561 tablet for oral administration
- Active substance:** TEZ (VX-661) and IVA (VX-770)
Activity: CFTR corrector and potentiator (increased Cl⁻ secretion)
Strength and route of administration: 100-mg TEZ/150-mg IVA, film-coated fixed-dose combination (FDC) tablet for oral administration
- Active substance:** IVA (VX-770)
Activity: CFTR potentiator (increased Cl⁻ secretion)
Strength and route of administration: 150-mg film-coated tablet for oral administration
- Study Duration** Excluding the Screening Period, the study duration for each subject is 9 to 11 weeks for Parts 1 [REDACTED] and 15 to 17 weeks for Part 2.
- Study Design** This is a Phase 2 [REDACTED] randomized, double-blind, placebo- and TEZ/IVA-controlled, proof-of-concept study of VX-121. Study parts may be conducted in parallel or sequentially.
Randomization will be stratified by ppFEV₁. Schematics of the study design are shown in [Figure 2-1](#), [Figure 2-2](#), [REDACTED]
- Part 1: Subjects with F/MF genotypes**
Part 1 evaluates VX-121 in TC with TEZ/VX-561 as shown in [Figure 2-1](#).
The Washout Period (18 ± 3 days) is included to enable a more thorough evaluation of VX-121 exposure-response relationships by conducting PK and PD assessments during the VX-121 washout.

Planned Doses

- TC-5 mg is optional. The planned VX-121 doses of 5 mg, 10 mg, and 20 mg qd may be adjusted based on emerging data from subjects with CF in Part D of Study VX17-121-001 (Study 001). However, no more than 3 dose levels of VX-121 will be evaluated, and the highest dose will not exceed 20 mg qd.
- The dosage of TEZ and VX-561 will be TEZ 100 mg daily (qd) and VX-561 150 mg qd.

Figure 2-1 VX18-121-101 Study Design for Part 1 (F/MF Genotypes)

	Treatment Period (4 weeks)	Washout Period (18 ± 3 days)	
Screening Period (4 weeks)	TC-20 mg (VX-121/TEZ/VX-561) N = 18	TEZ/ VX-561	Safety Follow-up Period (4 weeks)
	TC-10 mg (VX-121/TEZ/VX-561) N = 18		
	TC-5 mg (VX-121/TEZ/VX-561) N = 9		
	Triple Placebo N = 9	Dual Pbo	

Part 2 (Optional): Subjects with F/F genotype

Part 2, an optional part of the study, which will be conducted at the sponsor’s discretion, evaluates VX-121 in TC with TEZ/VX-561 as shown in Figure 2-2.

[figure not shown]
All subjects are required to complete the TEZ/IVA Run-in Period to establish a reliable on-treatment (TEZ/IVA) baseline. The 4-week Washout Period is included to evaluate the effect on PD and efficacy endpoints as subjects step down from TC to TEZ/IVA, after the VX-121 washout.

[figure not shown]
Planned Doses

- Part 2 will evaluate the same VX-121 dose (20 mg qd) used in Part 1. This dose may be adjusted downward based on emerging data from Part D of Study 001.
- The dosage of TEZ and VX-561 will be TEZ 100 mg qd and VX-561 150 mg qd.
- The dosage of TEZ/IVA will be TEZ 100 mg qd/IVA 150 mg every 12 hours (q12h).

Figure 2-2 VX18-121-101 Study Design for Part 2 (F/F Genotype)

	Run-in Period (4 weeks)	Treatment Period (4 weeks)	Washout Period (4 weeks)	
Screening Period (4 weeks)	TEZ/IVA	TC-20 mg (VX-121/TEZ/VX-561) N = 18	TEZ/IVA	Safety Follow-up Period (4 weeks)
		Placebo + TEZ/IVA N = 9		

Assessments **Safety:** AEs, clinical laboratory assessments, clinical evaluation of vital signs, ECGs, physical examinations, spirometry
Efficacy: Spirometry, CFQ-R respiratory domain
PD: Sweat chloride
PK: VX-121, TEZ, VX-561, [REDACTED], and relevant metabolites
[REDACTED]

Statistical Analyses A sample size of 18 subjects per treatment group provides at least 90% power to detect a mean within-treatment change of 7 percentage points. These calculations assumed a standard deviation of 8 percentage points for the absolute change from baseline in ppFEV₁.

To analyze the absolute change from baseline in ppFEV₁ through Day 29, a primary endpoint in Parts 1, 2, [REDACTED] a mixed-effects model for repeated measures (MMRM) with change from baseline for ppFEV₁ at Days 15 and 29 as the dependent variable will be performed for each part. The null within-group hypothesis of no difference in the mean absolute change from baseline through Day 29 for ppFEV₁, in all treatment groups, by part, will be tested using MMRM. The adjusted means and 2-sided 95% CIs of the average treatment effects through Day 29 for all within-group comparisons will be estimated within MMRM. *P* values will also be provided for these comparisons. All ppFEV₁ hypothesis tests will be performed within the MMRM framework at a 5% alpha level, with appropriate adjustment for baseline covariates.

P values reported for all endpoints other than the primary endpoint should be considered nominal as no adjustment for multiplicity will be performed.

Descriptive analyses will be provided for the safety data comprising AEs, clinical laboratory assessments, ECGs, vital signs, and spirometry; no statistical hypothesis testing will be performed. The PK results for VX-121, TEZ, VX-561, [REDACTED] and relevant metabolites will be reported with descriptive statistics.

IDMC Reviews An independent data monitoring committee (IDMC) will conduct safety reviews of study data as outlined in the IDMC charter.

3 SCHEDULE OF ASSESSMENTS

Schedules of assessments are in Table 3-1, Table 3-2, [REDACTED]

Table 3-1 Study VX18-121-101: Part 1, Screening, Treatment Period, Washout Period, and Safety Follow-up Visit

Event/Assessment ^a	Screening Visit ^b	Treatment Period					Washout Visit	ETT Visit ^c	Safety Follow-up 28 (± 7) Days After Last Dose of Study Drug ^d
	Day -28 to Day -1	Day 1	Day 2 ^e	Day 8 (± 1 day)	Day 15 (± 2 days)	Day 29 (± 2 days)	Day 47 (± 3 days)		
Outpatient visits	X	X	X	X	X	X	X	X	X
Informed consent	X								
Randomization ^f		X							
Demographics	X								
Medical history	X								
CFQ-R ^{g,h}		X			X	X			
Weight ⁱ	X	X		X	X	X		X	X
Height ⁱ	X								
Vital signs ^j	X	X	X	X	X	X	X	X	X
Pulse oximetry ^j	X	X	X	X	X	X	X	X	X
Physical examination ^k	Complete	Abbrev.		Abbrev.	Abbrev.	Abbrev.		Complete	Complete
Standard 12-lead ECG ^l	X	X		X	X	X		X	X
Sweat chloride ^{h,m}	X	X			X	X	X ⁿ	X	X

^a All assessments will be performed before dosing, unless noted otherwise. Assessments that are collected before and after dosing will only be collected once if study drug is not administered on the day of the visit (i.e., premature discontinuation of study drug treatment).

^b All screening results must be reviewed before randomization, unless noted otherwise.

^c If the subject prematurely discontinues study drug, an ETT Visit should be scheduled as soon as possible after the decision to terminate study drug treatment (Section 9.1.6). A final PK sample will be drawn from subjects who discontinue study drug for any reason (except withdrawal of consent). Safety assessments may also be performed at the discretion of the investigator..

^d Study drug refers to VX-121, TEZ, VX-561, and matching placebos.

^e Approximately 20 subjects enrolled in the study will have spirometry performed at 24 hours (± 2 hours) after the first dose. Only subjects participating in this spirometry assessment are required to complete the Day 2 Visit; this assessment should be performed predose on Day 2. Vertex will work with study sites to manage the allocation of subjects participating in the 24-hour postdose spirometry assessment. See Section 11.5.1 for more details.

^f Randomization may occur on the previous day (Day -1) after eligibility has been confirmed.

^g The CFQ-R must be completed before any other assessments scheduled at relevant visits.

^h The predose assessment on Day 1 may be performed on the previous day (Day -1) if randomization has occurred.

ⁱ Weight and height will be measured with shoes off.

^j Vital signs and pulse oximetry will be collected after the subject has been at rest for at least 5 minutes (Sections 11.6.3 and 11.6.4).

^k Complete and abbreviated PEs are described in Section 11.6.3.

^l Standard 12-lead ECGs will be performed in the supine position after the subject has been at rest for at least 5 minutes (Section 11.6.5). The ECG will be done before any other procedures that may affect heart rate, such as blood draws. ECGs collected on Day 1 before dosing will be performed in triplicate.

^m See Section 8.1 for information about the sweat chloride assessment for study eligibility.

ⁿ Sweat chloride and ppFEV₁ assessments should be done within 2 hours before study drug dosing in the morning (Sections 11.3 and 11.5.1).

Table 3-1 Study VX18-121-101: Part 1, Screening, Treatment Period, Washout Period, and Safety Follow-up Visit

Event/Assessment ^a	Screening Visit ^b	Treatment Period					Washout Visit	ETT Visit ^c	Safety Follow-up 28 (± 7) Days After Last Dose of Study Drug ^d
	Day -28 to Day -1	Day 1	Day 2 ^e	Day 8 (± 1 day)	Day 15 (± 2 days)	Day 29 (± 2 days)	Day 47 (± 3 days)		
Spirometry ^o	X	X	X	X	X	X	X ⁿ	X	X
Urinalysis ^h	X	X		X	X	X		X	X
β-hCG ^q	serum	urine				urine		serum	serum
CFTR genotype ^r	X								
FSH ^s	X								
Serum chemistry and hematology ^h	X	X		X	X	X		X	X
Coagulation ^h	X	X		X	X	X		X	X
PK sampling ^u		X	X	X	X	X	X	X	

^o Spirometry may be performed pre- or post-bronchodilator at the Screening Visit. Spirometry will be performed pre-bronchodilator, before the morning dose of study drugs, and should be performed at approximately the same time at every other study visit.

^q The serum β-hCG test is to be performed for all female subjects at screening. Subsequent urine or serum β-hCG tests are to be performed as indicated for women of childbearing potential. A definition of non-childbearing potential is provided in Section 11.6.7.1.

^r CFTR genotyping will be performed for all subjects. If the screening CFTR genotype result is not received before randomization, a previous CFTR genotype laboratory report may be used to establish eligibility (Section 8.1).

^s FSH will be measured for any suspected postmenopausal female subjects with at least 12 months of continuous spontaneous amenorrhea.

^u Blood samples will be collected for PK analysis of VX-121, TEZ and metabolites, and VX-561 and metabolites. On Day 1, samples will be collected before dosing (0 hours) and at 1, 2, 4, 6, and 8 hours after dosing (relative to the morning dose). Samples will also be collected at 24 hours after dosing on Day 1 (i.e., predose on Day 2) for subjects participating in the Day 2 Visit (see Footnote e). On Days 8, 15, and 29, a predose sample will be collected before the morning dose of study drug (0 hours). On Day 47, a single predose sample will be collected before study drug dosing in the morning. Acceptable PK sampling windows are provided in Table 11-1. At the ETT Visit, a single blood sample for PK analysis will be collected.

Table 3-1 Study VX18-121-101: Part 1, Screening, Treatment Period, Washout Period, and Safety Follow-up Visit

Event/Assessment ^a	Screening Visit ^b	Treatment Period					Washout Visit	ETT Visit ^c	Safety Follow-up 28 (± 7) Days After Last Dose of Study Drug ^d
	Day -28 to Day -1	Day 1	Day 2 ^e	Day 8 (± 1 day)	Day 15 (± 2 days)	Day 29 (± 2 days)	Day 47 (± 3 days)		
TEZ/VX-561 or placebo dosing ^v		Day 1 through Washout Visit							
VX-121 or placebo dosing ^w		Day 1 through Day 29							
Adverse events	Continuous from signing of ICF through Safety Follow-up Visit								
Medications review ^x	Continuous from signing of ICF through Safety Follow-up Visit								
Treatment and procedures review	Continuous from signing of ICF through Safety Follow-up Visit								

^v The last dose of study drug will be the morning dose at the Washout Visit.

^w The last dose of study drug will be the morning dose on the Day 29 Visit.

^x All medications taken from 28 days before the Screening Period through the end of the study will be recorded.

Table 3-2 Study VX18-121-101: Part 2 (Optional), Screening, Run-in Period, Treatment Period, Washout Period, and Safety Follow-up Visit

Event/Assessment ^a	Screening Visit ^b	Run-in Period		Treatment Period ^c				Washout Period		ETT Visit ^d	Safety Follow-up 28 (± 7) Days After Last Dose of Study Drug ^{e,f}
	Day -56 to Day -29	Day -28 (± 1 day)	Day -14 ^g (+ 13 days)	Day 1	Day 8 (± 1 day)	Day 15 (± 2 days)	Day 29 (± 2 days)	Day 43 (± 3 days)	Day 57 (± 3 days)		
Outpatient visits	X	X	X	X	X	X	X	X	X	X	X
Informed consent	X										
Randomization ^h				X							
Demographics	X										
Medical history	X										
CFQ-R ^{i,j}				X		X	X		X		
Weight ^k	X	X		X	X	X	X	X	X	X	X
Height ^k	X										
Vital signs ^l	X	X		X	X	X	X	X	X	X	X
Pulse oximetry ^l	X	X		X	X	X	X	X	X	X	X
Physical examination ^m	Complete	Abbrev.		Abbrev.	Abbrev.	Abbrev.	Abbrev.		Abbrev.	Complete	Complete
Standard 12-lead ECG ⁿ	X	X		X	X	X	X	X	X	X	X
Sweat chloride ^o	X		X	X		X	X	X ^p	X ^p	X	
Spirometry ^q	X		X ^r	X	X	X	X	X ^p	X ^p	X	X

^a All assessments will be performed before dosing, unless noted otherwise. Assessments that are collected before and after dosing will only be collected once if study drug is not administered on the day of the visit (i.e., premature discontinuation of study drug treatment).

^b All screening results must be reviewed before the Run-in Period.

^c To qualify to continue into the Treatment Period, conditions for entry must be satisfied (Section 9.1.3).

^d If the subject prematurely discontinues study drug, an ETT Visit should be scheduled as soon as possible after the decision to terminate study drug treatment (Section 9.1.6). A final PK sample will be drawn from subjects who discontinue study drug for any reason (except withdrawal of consent). Safety assessments may also be performed at the discretion of the investigator.

^e Part 2 subjects who meet criteria specified in Section 9.1.5 will not have a Safety Follow-up Visit.

^f Study drug refers to VX-121, TEZ, VX-561, TEZ/IVA, IVA, and matching placebos.

^g Assessments at this visit may be performed postdose.

^h Randomization may occur on the previous day (Day -1) after all conditions for entering the Treatment Period have been confirmed (Section 9.1.3).

ⁱ The CFQ-R must be completed before any other assessments scheduled at relevant visits.

^j The predose assessment on Day 1 may be performed on the previous day (Day -1) if randomization has occurred.

^k Weight and height will be measured with shoes off.

^l Vital signs and pulse oximetry will be collected after the subject has been at rest for at least 5 minutes (Sections 11.6.3 and 11.6.4).

^m Complete and abbreviated PEs are described in Section 11.6.3.

ⁿ Standard 12-lead ECGs will be performed in the supine position after the subject has been at rest for at least 5 minutes (Section 11.6.5). The ECG will be done before any other procedures that may affect heart rate, such as blood draws. ECGs collected on Day 1 before dosing will be performed in triplicate.

^o See Section 8.1 for information about the sweat chloride assessment for study eligibility.

^p Sweat chloride and ppFEV₁ assessments should be done within 2 hours before study drug dosing in the morning (Sections 11.3 and 11.5.1).

^q Spirometry may be performed pre- or post-bronchodilator at the Screening Visit. Spirometry will be performed pre-bronchodilator, before the morning dose of study drugs (except at the Day -14 Visit when spirometry may be performed postdose), and should be performed at approximately the same time at every other study visit. See Section 11.5.1 for more details.

Table 3-2 Study VX18-121-101: Part 2 (Optional), Screening, Run-in Period, Treatment Period, Washout Period, and Safety Follow-up Visit

Event/Assessment ^a	Screening Visit ^b	Run-in Period		Treatment Period ^c				Washout Period		ETT Visit ^d	Safety Follow-up 28 (± 7) Days After Last Dose of Study Drug ^{e,f}
	Day -56 to Day -29	Day -28 (± 1 day)	Day -14 ^g (+ 13 days)	Day 1	Day 8 (± 1 day)	Day 15 (± 2 days)	Day 29 (± 2 days)	Day 43 (± 3 days)	Day 57 (± 3 days)		
Urinalysis ⁱ	X	X		X	X	X	X	X	X	X	X
β-hCG [†]	serum	urine		urine			urine		urine	serum	serum
CFTR genotype ^u	X										
FSH ^v	X										
Serum chemistry and hematology ^j	X	X		X	X	X	X	X	X	X	X
Coagulation ^j	X	X		X	X	X	X			X	X

^r The ppFEV₁ assessment for stratification of randomization will be done at the Day -14 Visit. See Section 9.1.2 and Section 9.2.

[†] The serum β-hCG test is to be performed for all female subjects at Screening. Subsequent urine or serum β-hCG tests are to be performed as indicated for women of childbearing potential. A definition of non-childbearing potential is provided in Section 11.6.7.1.

^u CFTR genotyping will be performed for all subjects. If the screening CFTR genotype result is not received before the Run-in Period, a previous CFTR genotype laboratory report may be used to establish eligibility (Section 8.1).

^v FSH will be measured for any suspected postmenopausal female subjects with at least 12 months of continuous spontaneous amenorrhea.

Table 3-2 Study VX18-121-101: Part 2 (Optional), Screening, Run-in Period, Treatment Period, Washout Period, and Safety Follow-up Visit

Event/Assessment ^a	Screening Visit ^b	Run-in Period		Treatment Period ^c				Washout Period		ETT Visit ^d	Safety Follow-up 28 (± 7) Days After Last Dose of Study Drug ^{e,f}
	Day -56 to Day -29	Day -28 (± 1 day)	Day -14 ^g (+ 13 days)	Day 1	Day 8 (± 1 day)	Day 15 (± 2 days)	Day 29 (± 2 days)	Day 43 (± 3 days)	Day 57 (± 3 days)		
PK sampling ^x				X	X	X	X	X	X	X	
TEZ/IVA dosing ^y		Day -28 to evening on Day -1						Evening of Day 29 through Day 57			
VX-121/TEZ/VX-561 or TEZ/IVA dosing ^z				Day 1 through Day 29							
Adverse events	Continuous from signing of ICF through Safety Follow-up Visit										
Medications review ^{aa}	Continuous from signing of ICF through Safety Follow-up Visit										
Treatment and procedures review	Continuous from signing of ICF through Safety Follow-up Visit										

^x Blood samples will be collected for PK analysis of VX-121, TEZ and metabolites, and VX-561 and metabolites. On Day 1, samples will be collected before dosing (0 hours) and at 1, 2, 4, 6, and 8 hours after dosing (relative to the morning dose). On Days 8, 15, and 29, a predose sample will be collected before the morning dose of study drug (0 hours). On Days 43 and 57, a single blood sample for PK analysis will be collected before the morning dose of TEZ/IVA. Acceptable PK sampling windows are provided in [Table 11-1](#). At the ETT Visit, a single blood sample for PK analysis will be collected.

^y The final dose during the Run-in Period will be administered on Day -1, the evening before the Day 1 Visit. The final dose during the Washout Period will be the morning dose on the Day 57 Visit.

^z The last dose of VX-121/TEZ/VX-561 or TEZ/IVA will be the morning dose on the Day 29 Visit.

^{aa} All medications taken from 28 days before the Screening Period through the end of the study will be recorded.

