9.1.6 Early Termination of Treatment

If the subject prematurely discontinues study treatment, an Early Termination of Treatment (ETT) Visit should be scheduled as soon as possible after the subject decides to terminate study drug. Subjects who prematurely discontinue study treatment will also be required to complete the Safety Follow-up Visit, approximately 28 days after their last dose of study drug. The assessments performed at the Safety Follow-up Visit are listed in [Table 3-1](#), [Table 3-2](#), [REDACTED]

Subjects who discontinue from study drug dosing for any reason (except withdrawal of consent) will have a final PK blood sample drawn as soon as possible after the decision to discontinue study drug is made. Additional safety assessments may also be performed at the discretion of the investigator, including possible consultation with a specialist consultant. The Vertex medical monitor will be informed about these additional assessments, and any additional data collected (e.g., as the result of an outside consultation) will be considered part of the study record to provide the most complete safety profile of the study drug.

If the ETT Visit occurs 3 weeks or later following the last dose of study drug, then the ETT Visit will replace the Safety Follow-up Visit, and a separate Safety Follow-up Visit will not be required.

If the subject withdraws consent for the study, no further assessments should be performed, and no additional data should be collected. Vertex may retain and continue to use any data and samples collected before such withdrawal of consent.

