9.9 Removal of Subjects

Subjects may withdraw from the study at any time at their own request. Subjects may be withdrawn from study drug treatment at any time at the discretion of the investigator or Vertex

for safety, behavior, noncompliance with study procedures, or administrative reasons. A subject who withdraws from study drug treatment will continue to be followed unless the subject withdraws consent.

Subjects will discontinue from study drug dosing and the investigator will notify the medical monitor if any of the following occur

- Pregnancy
- Meets any of the stopping (discontinuation) criteria (Section 9.8) or has other unacceptable toxicity as determined by the investigator

Subjects who are withdrawn from study drug dosing will complete assessments as described in Section 9.1.6 and may have additional PK samples collected as deemed appropriate by the investigator in consultation with the Vertex medical monitor. Consideration should be given to the need for additional safety assessments as described in Section 9.1.6. The investigator will use clinical judgment to determine whether assessments after study drug discontinuation should occur while the subject remains confined in the clinical unit or can be completed as outpatient visits.

Subjects who have been enrolled and whose screening *CFTR* genotype does not confirm study eligibility must be discontinued from the study, even if a previous *CFTR* genotype laboratory report was used to establish eligibility.

If a subject does not return for a scheduled visit, reasonable effort will be made to contact the subject. In any circumstance, reasonable effort will be made to document subject outcome. The investigator will inquire about the reason for withdrawal, request that the subject return all unused investigational product(s), request that the subject return for a Safety Follow-up Visit, if applicable (see Section 9.1.5), and follow up with the subject regarding any unresolved AEs.

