### **8.3 Efficacy Analysis**

All efficacy analyses described in this section will be based on the FAS.

The analysis will include all available measurements through the last scheduled on-treatment visit including measurements after treatment discontinuation, per the visit windowing rules described in [Appendix A](#).

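### CFQ-R is not scheduled at the ETT Visit in either part, so a subject who stops study drug before Day 15 has no required post-baseline score

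*Protocol*

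**What the plan says.** The protocol synopsis names two efficacy assessments: "Efficacy: Spirometry, CFQ-R respiratory domain". The CFQ-R secondary endpoint is "Absolute change in Cystic Fibrosis Questionnaire-Revised (CFQ-R) respiratory domain score from baseline at Day 29".

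Table 3-1 (Part 1) marks CFQ-R on Days 1, 15 and 29. Table 3-2 (Part 2) marks it on Days 1, 15, 29 and 57. The ETT and Safety Follow-up cells are blank for CFQ-R in both tables. Spirometry and sweat chloride are marked at ETT in both. The footnote to the CFQ-R row, "The CFQ-R must be completed before any other assessments scheduled at relevant visits", concerns sequence within a visit; the evidence for this point is the blank cell.

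For subjects who stop study drug, Section 9.1.6 calls for an ETT Visit and adds: "Subjects who prematurely discontinue study treatment will also be required to complete the Safety Follow-up Visit, approximately 28 days after their last dose of study" (the last word of the sentence is left off here). Section 9.9 refers back: "Subjects who are withdrawn from study drug dosing will complete assessments as described in Section 9.1.6". Neither section requires the remaining Day 15 or Day 29 visits.

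SAP 8.3 bases efficacy analyses on whatever measurements exist through the last scheduled on-treatment visit, "including measurements after treatment discontinuation, per the visit windowing rules described in" Appendix A. SAP 8.3.2.2.2 analyses CFQ-R with an MMRM similar to the primary one. The primary model (SAP 8.3.1.2) uses Days 15 and 29, assumes missing at random and does not impute. No sensitivity analysis is planned for the primary variable, and none is listed for CFQ-R.

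**The concern.** The ETT Visit is the one visit planned promptly after a subject stops, and the questionnaire is not given there. The SAP's CFQ-R windows would accept a score from that visit, but the schedule does not produce one. A subject who stops early stays in the Full Analysis Set and may contribute no record to the CFQ-R model.

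What is at stake is the within-group change in a secondary endpoint. Under missing at random, the model treats the absent scores as if they resembled those of comparable subjects who stayed. If some subjects stop because they feel worse, that assumption flatters the result, and nothing in the plan would show by how much. The groups are small (18 or 9), so one missing subject is a visible share.

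**Working it through.** No stated figure in the plan bears on this point. The only power statement is for ppFEV₁ (n = 18, change 7, SD 8, two-sided 5%). A one-sample t calculation gives 93.8%, which agrees with the stated minimum of 90%. No power is given for CFQ-R.

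**Schedule against analysis windows** (Protocol Tables 3-1 and 3-2; SAP Table 11-1, study days after the first Treatment Period dose)

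| Measure | Marked at ETT | Day 15 window | Day 29 window, Part 1 / Part 2 |
|---|---|---|---|
| CFQ-R | No | [1, 22] | (22, 61] / (22, 43] |
| Sweat chloride | Yes | [1, 22] | (22, 38] / (22, 36] |
| Spirometry | Yes | (12, 22]; up to Day 12 goes to Day 8 | (22, 38] / (22, 36] |

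The clean contrast is with sweat chloride. An ETT Visit on Day 5 gives a sweat chloride value that enters its model at Day 15, while CFQ-R, with the same window, has no value. Spirometry differs: an ETT ppFEV₁ on Day 5 falls in the Day 8 window and is also outside the primary MMRM.

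**Required CFQ-R scores by time of stopping**

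- Before Day 15: none after baseline, in either part.
- After the Day 15 score and before Day 29: Day 15 only. The subject enters the model, but without the endpoint visit.

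**Illustrative loss of subjects.** The documents give no dropout rate, so the rates p are assumptions. Expected loss is n × p; the chance of at least one is 1 − (1 − p)^n.

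- n = 18: p = 5% gives 0.9 expected and a 60% chance of at least one; p = 10% gives 1.8 and 85%.
- n = 9: p = 5% gives 0.45 and 37%; p = 10% gives 0.9 and 61%.

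One subject is 1/18 = 5.6% or 1/9 = 11.1% of a group. The standard error rises by √(18/17) = 1.029 or √(9/8) = 1.061.

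**Illustrative overstatement** = share without a score × mean shortfall against what the model assumes for them. Both inputs are assumptions.

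- 10 points: 0.05, 0.10 and 0.15 × 10 = 0.5, 1.0 and 1.5 points.
- 20 points: 1.0, 2.0 and 3.0 points.

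For subjects with a Day 15 score, the relevant shortfall is the part that this score does not already predict, so the product is simplest for those who stop before Day 15.

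**What the windows would do with an ETT score.** The SAP Table 11-1 notes select the measurement nearest the target day and, on a tie, the latest.

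- ETT by Day 22 with no Day 15 score: placed at Day 15.
- ETT after Day 22, inside the Day 29 window: placed at Day 29 when no closer score exists. In Part 2, a score after Day 43 goes to Day 57.
- Day 15 score on target and ETT on Day 18: distances 0 and 3, so the ETT score is set aside and Day 29 stays missing. If the Day 15 visit was held on Day 13 (the protocol allows ±2 days), an ETT score on Day 16 would be chosen (distance 1 against 2), but Day 29 would still be missing.

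**The case against.** Several parts of the opposing case stand.

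- *Off-drug attendance is not excluded.* Section 9.9 says that subjects withdrawn from study drug go on being followed. Footnote a of both schedule tables and Section 10.7.1 also contemplate subjects in the study after stopping. Some sites may therefore collect Day 15 or Day 29 CFQ-R off drug. No section requires it, so the point is about required scores. A reader might infer that early stoppers never give a post-baseline score; the documents do not establish that.
- *There is no conflict with the SAP.* A reader might take SAP 8.3 to promise post-discontinuation CFQ-R data. It covers only data that exist and does not say each measure is collected after stopping.
- *CFQ-R is not alone in losing early stoppers.* A reader might infer that ppFEV₁ is retained where CFQ-R is lost. For an ETT Visit up to Day 12 it is not. The protocol classes sweat chloride as pharmacodynamic, although the SAP treats it among the secondary efficacy variables, and redacted rows prevent any claim about every efficacy measure.
- *Upward bias is not shown.* Section 9.9 also allows withdrawal for administrative reasons or noncompliance, which need not mean worse symptoms.
- *The consequence is limited.* CFQ-R is a secondary endpoint with nominal P values in a four-week proof-of-concept study. Section 9.10 allows replacement of subjects withdrawn for nonsafety reasons, which restores numbers though not the missing scores.

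None of this fills the blank cell or explains why CFQ-R is left out of a visit at which the other two measures are taken.

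**Conclusion.** The gap is real and small. Neither schedule table asks for CFQ-R at ETT, and Section 9.1.6 requires no later visit at which CFQ-R is scheduled. A subject who stops before Day 15 may therefore be absent from the CFQ-R model, and one who stops between Days 15 and 29 may lack the endpoint visit. The finding rests on off-drug visits not being required; where they are attended, the gap narrows.

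Any overstatement depends on stoppers scoring below what the missing-at-random model assumes. At 5% to 15% stopping and a 10-point shortfall it would be 0.5 to 1.5 points, but neither input comes from the documents. The documents do not support reading this as an error in the SAP or as a demonstrated bias. It is an inexpensive improvement to a secondary endpoint.

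**What to change.** Mark CFQ-R at the ETT Visit in Tables 3-1 and 3-2, completed first at that visit under the existing footnote. In Part 2, limit it to ETT visits after the first Treatment Period dose, because the analysis concerns change from the Treatment Period baseline.

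No window needs to change for these scores to be used. To recover the Day 29 score for subjects whose ETT Visit falls on Days 16 to 22, the protocol would also have to ask for the Day 29 CFQ-R off drug. If neither change is made, the SAP should state that the CFQ-R analysis relies on missing at random with little or no required data after discontinuation.

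The cost is one cell in each table and a short questionnaire, already in use, at a visit already held. The downside is that some scores taken soon after stopping, well before Day 15, would be analysed as Day 15; the SAP windows already do this for sweat chloride.
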